10.6.3 Concomitant Medication and Supportive Care Guidelines

At each study visit/contact, the investigator will ask the participants about any medication taken, including herbals, vitamins and holistic/naturopathic medications, concomitant medication, including vaccines, and any other medication relevant to the protocol, including any specifically contraindicated will be recorded in the eCRF device with trade name and/or generic name of the medication, medical indication, start and end dates of treatment. Concomitant medications will include but are not limited to:

- Antibiotics,
- Over the counter (OTC)
- Prescription meds.

10.6.4 Laboratory Evaluations/Assays

Whole blood samples will be collected via venipuncture for clinical safety laboratory evaluations and BCG response assays. A total of ~730mls (~3 cups) will be drawn for the entire study. At the screening visit (visit 1) and Days 0 (visit 2), 1 (visit 3), 2 (visit 4), 3 (visit 5), 4 (visit 6), 8 ± 1 (visit 7), 15 ± 1 (visit 8), 28 ± 1 (visit 9), 56 ± 2 (visit 10), 84 ± 3 (visit 11), 98 ± 1 (visit 12), 112 ± 1 (visit 14), and 114 ± 1 (visit 15), these standard blood draws will be collected from each participant to perform immunogenicity and humoral assays.

Clinical safety assessments

Blood samples for clinical safety laboratory evaluations (WBC, hemoglobin, platelet count, ALT (SGPT), creatinine) will be collected from each subject prior to administration of Tice® BCG at the screening visit (visit 1). These parameters must meet protocol-defined eligibility criteria to be enrolled and receive Tice® BCG. Additional clinical safety laboratory evaluations may be deemed necessary during the study.

Measuring BCG response

Skin biopsy (via XX)

Skin biopsies will be taken to quantify BCG bacteria. The ID challenge site will be biopsied on Days 3, 8, 15 and 56 (visits 5, 9, 10, and 12) after Tice® BCG administration. A 4mm skin biopsy using the punch method will be taken at the ID challenge site. A local anesthetic injection will be given to numb the site. Gel foam will be used to close the biopsy area. A medically licensed research team member will perform the biopsy.

The number of viable BCG bacteria will be measured on Day 3 from the skin biopsy by 1) quantitative CFU plating, 2) the numbers of genomes of BCG by quantitative real time PCR, and if sufficient material is available, by 3) additional assays may be performed to assess the integrity of the immune system.

Blood samples (via venipuncture)

- Serum will be collected on Days: 0, 1, 2, 3, 4, 8 ± 1 , 15 ± 1 , 28 ± 1 56 ± 2 , and 84 ± 3 , scheduled visits will be collected for inflammatory markers (IL-2, IL-4, IL-5, IL-8, IL-10, INF γ , 1L-12p70, 1L-17A, IL-1, IL-6 and TNF- α levels) using Cytokine BeadArray, and clinical testing for acute phase reactants (ESR and CRP).

- Blood will be collected for ELISPOT/ICS and additional assays to assess the integrity of the immune system on Days: 0, 8±1, 28±1, 56±2, 84±3, and 114±1. Whole blood will be collected for RNA seq studies on Days: 0, 1, 2, 3, 4, 8±1, 15±1, 28±1, 56±2, and 84±3. Plasma obtained from the density gradients used to purify PBMCs will be collected and frozen on Days: 0, 1, 8±1, 15±1, 28±1, 56±2, 84±3, and 114±1. Anticoagulated whole blood will be collected for dendritic cell (DC), monocyte and natural killer (NK) cell assays on Days: 1, 4, 8±1, 15±1, 28±1, 56±2, and 114±1.

10.7 **Photographs**

Photographs of the ID challenge site will be taken at each follow-up visit after Tice® BCG administration starting on Day 4 through Day 56±2. If the participant has any abnormality and does not have a well-healed scar, or the site is open and/or draining, photographs will continue once/week from the day the abnormality was identified until it has resolved. All subjects will have a final photograph of the ID challenge site on Day 114±1 or upon early termination.

10.8 **PPD Skin Test**

2-Step PPD skin test will be performed and/or accessed on Days: 98±1, 100±1, 112±1 and 114±1. If the first PPD skin test result is negative, then the second PPD skin test will be performed 2-4 weeks later. If either of the 2-Step PPD skin test results is positive, defined as ≥ 10 mm of induration, then the subject will have a QuantiFERON®-TB Gold Test performed to determine TB infection or BCG immunity.

10.9 **Memory Aid eCRF Device and AE/SAE Recording Training**

Participants will be instructed on how to use the initial and on-going subject memory aids eCRF device and how to measure and record AEs/SAEs, concomitant medication and other health status information.

11.0 STUDY SCHEDULE

11.1 **Participant Procedures Schedule**

See Appendix B

11.2 **Clinic Visit Schedule**

Screening visit: A single visit between Days -42 and -1 (visit 1)

- Informed Consent
- Review medical history,
- Review concomitant medications,
- Collect vital signs (oral temperature, pulse, blood pressure),
- Collect height and weight (to calculate BMI),
- General examination,
- Collect urine for dipstick for protein < 1 and negative for glucose and chlamydia/gonorrhea test,

- Blood draw (29mls (6 teaspoons (tsp)) for testing HIV, hepatitis B surface antigen, antibody to hepatitis C virus, syphilis and QuantiFERON®-TB Gold Test. Results of these screening tests must be negative,
- Pregnancy tests for females of childbearing potential (must be negative for eligibility).
 - Serum pregnancy test at screening,
 - Urine pregnancy test within 24 hours prior to enrollment and receipt of Tice® BCG and INH.

Day 0 (clinic visit 2)

- Administration of BCG 2×10^6 cfu Tice® BCG: one intradermal injection in the deltoid region,
 - * Following administration of Tice® BCG, intradermal (ID) site reactions will be assessed for at least 30 minutes.
- Blood draw via venipuncture for immunogenicity and mycobacteria assays: 114.5mls (8 tbs),
- Participants will be instructed on how to use the initial and on-going subject memory aids eCRF device and how to measure and record AEs/SAEs prior to discharge from the clinic,
- In addition, subjects will be instructed to keep the ID challenge site covered with a dressing (sterile gauze, etc.) and all dressings that have been used to cover the ID challenge site will be collected in sealable clear plastic bags. These materials will be collected from subjects at follow-up visits and properly disposed of as biohazard waste. Subjects will also be counseled to avoid any direct contact of drainage with an immunosuppressed person.

Day 1 (clinic visit 3), Day 2 (clinic visit 4), and Day 3 (clinic visit 5)

- Assess ID challenge site,
- Day 3 (clinic visit 5) only: skin biopsy,
- Review health status and AEs/SAEs that were recorded on the memory aid eCRF device,
- Blood draws via venipuncture for immunogenicity and mycobacteria assays:
 - Day 1: 6.5mls (1.5 tsp),
 - Day 2: 6.5mls (1.5 tsp),
 - Day 3: 6.5mls (1.5 tsp),
- Subjects will be reminded to record self-assessments on their redcap survey:
 - Oral temperature (optional)
 - Solicited local and systemic reactions recorded Days 1-114,
 - Unsolicited AEs/SAEs recorded Days 1-114,
 - Concomitant medications recorded Days 1-114.
- Collection of used dressing/gauze.

Days 4 (clinic visit 6), 5 (clinic visit 7), 6 (clinic visit 8), 8 ± 1 (clinic visit 9), 15 ± 1 (clinic visit 10), and 28 ± 1 (clinic visit 11)

- INH dosing days 4, 5, and 6 only: For the 5 participants assigned to Group 1, they will take INH: oral tablets of either three 100mg tablets (total 300mg) or one 300mg tablet for 3 days post BCG dosing,
- Days 8 ± 1 (clinic visit 9) and 15 ± 1 (clinic visit 10) only: Repeat skin biopsy,
- Assess ID challenge site,
- Review health status and AEs/SAEs that were recorded on the memory aid eCRF device,
- Review concomitant medications,
- Assess for lymphadenopathy if indicated based on review of interim medical history and clinical assessment,

- Targeted physical exam and clinical assessment may be performed if indicated based on review of interim medical history, reactogenicity (as applicable),
- Blood draws via venipuncture for immunogenicity and mycobacteria assays:
 - Day 4: 6.5mls (1.5 tsp),
 - Day 8±1: 74.5mls (5 tablespoons (tbs)),
 - Day 15±1: 56.5mls (4 tbs),
 - Day 28±1: 94.5mls (6 tbs),
- Collect used dressing/gauze,
- Photograph of ID challenge site.

Days 16-114±1

- On-going participant self-evaluations that will be recorded on their memory aid eCRF device for pain, tenderness and drainage. Participants can record their temperature if taken.

Days 56±2 (clinic visit 12) and 84±3 (clinic visit 13)

- Day 56±2 (clinic visit 12) only: Repeat skin biopsy
- Assess ID challenge site (if an abnormal BCG injection site is identified see Abnormal BCG Injection Site Procedures in section 11.3),
- Review health status and AEs/SAEs that were recorded on the memory aid eCRF device,
- Review concomitant medications,
- Assessments for lymphadenopathy if indicated based on review of interim medical history and clinical assessment,
- Targeted general exam and clinical assessment may be performed if indicated based on review of interim medical history, reactogenicity (as applicable),
- Blood draws via venipuncture for immunogenicity and mycobacteria assays:
 - Day 56±2: 94.5mls (6 tbs)
 - Day 84±3: 94.5mls (6 tbs)
- Collect used dressing/gauze,
- Photograph of ID challenge site.

Day 98±1 (clinic visit 14)

- Assess ID challenge site,
- Review health status and AEs/SAEs that were recorded on the memory aid eCRF device,
- Review concomitant medications,
- Blood draw via venipuncture for diagnostic assays: 4mls (1 tsp),
- PPD skin test.

Day 100±1 (clinic visit 15)

- Assess ID challenge site,
- Review health status and AEs/SAEs that were recorded on the memory aid eCRF device,
- Review concomitant medications,
- PPD skin test assessment.

*Day 120/134: If the first PPD skin test result is negative, then the second PPD skin test will be performed 2-4 weeks later. If either of the 2-Step PPD skin test results is positive, defined as ≥ 10

mm of induration, then the participant will have a QuantiFERON®-TB Gold Test performed to determine TB infection or BCG immunity.

Days 112±1 (clinic visit 16)

- Assess ID challenge site,
- Review health status and AEs/SAEs that were recorded on the memory aid eCRF device,
- Review concomitant medications,
- Blood draw via venipuncture for diagnostic assays: 4mls (1 tsp),
- PPD skin test.

Day 114±1 (clinic visit 17) End of Study

- General exam,
- Assess ID challenge site,
- Review health status and AEs/SAEs that were recorded on the memory aid eCRF device,
- Review concomitant medications,
- Blood draw via venipuncture for immunogenicity and humoral assays: 138mls (9.5 tbs),
- Photograph of ID challenge site,
- PPD skin test assessment,
- Participants returns memory aid eCRF devices.

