5.8 Potential Risks and Benefits

5.8.1 Known Potential Risks

Risks of BCG

The BCG vaccine continues to be the most widely distributed vaccine worldwide, generally provided to infants immediately after birth, so it is safe and well tolerated. Typically, most people will develop a small swelling (nodule) at the injection site that break open, release pus or blood-tinged discharge, and form an ulcer the size of a dime. The ulcer will heal over a period of weeks and forms a scar that remains for life. Occasionally, lymph nodes around the vaccination site can become tender to touch. “Flu-like” symptoms that are common to many vaccines includes fevers, chills, loss of appetite, muscle aches, and generally not feeling well can last 1-2 days.

A very small number of people (1 in 4 million) have an immediate allergic reaction to BCG. Symptoms include rash, swelling around the mouth, difficulty breathing. These can be treated with emergency medications. If severe, they can cause death.

There is a risk that by receiving the BCG vaccine, participants may develop a false positive tuberculin skin test (PPD) that will complicate the early diagnosis and treatment of latent (inactive) TB. However, a diagnosis of latent TB can be confirmed by other methods, including a clinical examination, chest x-ray, and blood test (IFN-g release assay).

Risks of Isoniazid (INH)

Participants who are administered Isoniazid may experience some side effects that include: numbness and tingling in the extremities, hepatitis (symptoms include loss of appetite, nausea, vomiting, fatigue, malaise, and weakness), nausea, vomiting, upset stomach, fever, and rash.

Participants will be closely monitored by study staff and necessary treatment will be administered to alleviate symptoms that may occur.

Risks of Intradermal Injection

Participants may experience: pain, swelling, redness, itching caused by the ID injection. There is potential for an infection at the ID challenge site.

Risks of Skin Biopsy

Participants may experience: pain, swelling, redness, bleeding and bruising at the biopsy site during and a day or two after, damage to the skin such as artery or nerve and possible scarring. There is potential for an infection at biopsy site or allergic reaction to the anesthetic or gel foam

used to close the biopsy site. Participants cannot swim in a chlorinated water until the gel foam has sufficiently closed the biopsy area.

Risks of Blood Draws

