11.3 Abnormal BCG Injection Site Procedures

The BCG injection site evaluations are scheduled from Day 0 to 84±3. However, signs of an abnormal injection site may present around Day 28. If an injection site does not have a well healed scar, or has an open and draining ulcer, then the subject will be asked to return to the clinic twice per/week from the time the abnormality is identified until it has resolved. At each of these visits the following evaluations will be completed: assessments of the ID challenge site, assessments for lymphadenopathy if indicated based on review of interim medical history and clinical assessment, as well as review AEs/SAEs, concomitant medications, and health status, and collect and dispose of returned biohazard materials. Photographs will be taken once per/week from the day of the abnormal assessment until it has resolved.

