15.2 Methods and Timing for Assessing, Recording, and Analyzing Safety Parameters

15.2.1 Adverse Events

Adverse Event (AE):

International Conference on Harmonisation (ICH) E6 defines an AE as any untoward medical occurrence in a patient or clinical investigation subject administered a pharmaceutical product regardless of its causal relationship to the study treatment. An AE can therefore be any unfavorable and unintended sign (including an abnormal laboratory finding), symptom, or disease temporally associated with the use of a medicinal (investigational) product. The occurrence of an AE may come to the attention of study personnel during study visits and interviews of a study treatment recipient presenting for medical care, or upon review by a study monitor.

All AEs, including local and systemic reactions, not meeting the protocol-defined criteria for serious adverse events (SAEs) should be captured on the appropriate data collection form and eCRF. Information to be collected for unsolicited AEs includes event description, date of onset, study clinician's assessment of severity and relationship to study product and alternate etiology (if not related to study product) (assessed only by those with the training and authority to make a diagnosis), date of resolution/stabilization of the event, seriousness and outcome. All AEs occurring while on study will be documented appropriately regardless of relationship. All AEs will be followed to adequate resolution.

Any medical condition that is present at the time that the subject is screened should be considered as baseline and not reported as an AE. However, if the severity of any pre-existing medical condition increases at any time during the study, it should be recorded as an AE.

All AEs must be graded for severity and assessed for relationship to study product (see definitions below). Adverse events characterized as intermittent require documentation of onset and duration of each episode. The start and stop date of each reported AE will be recorded on the appropriate data collection form and eCRF.

Severity of Event:

All AEs will be assessed by the site principal investigator or appropriate sub-investigator using the protocol-defined grading system (Section 15.2.2-15.2.3). For events not included in the protocol defined grading system, the following guidelines will be used to quantify severity:

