15.2.5 *Procedures to be Followed in the Event of Abnormal Laboratory Test Values or Abnormal Clinical Findings*

The site principal investigator is responsible for reporting all AEs/SAEs that are observed or reported during the study, regardless of their relationship to study product. AEs/SAEs, abnormal laboratory test values or abnormal clinical findings will be documented, reported and followed appropriately. Adverse events will be assessed through approximately 8 weeks following Tice® BCG administration. Serious adverse events will be assessed for the study duration.

15.3 **Reporting Procedures**

- Document AEs from Visit 02 (Day 0) through Visit 10 (Day 56±2).
- Document SAEs from Visit 02 (Day 0) through Visit 15 (Day 114±1).

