Appendix B: Participant Procedures Table

Clinic Visit	1 (Screening Visit)	2	3	4	5	6	7	8	9	10	11	12	13	14	15	16	17
Day	-42 to -1	0	1	2	3	4	5	6	8±1	15±1	28±1	56±2	84±3	98±1	100±1	112±1	114±1
Week		0							1	2	4	8	12	14		16	
Agents		BCG			INH	INH	INH										
Informed consent	X																
Medical history	X																
Height, weight: BMI	X																
Vitals (pulse, blood pressure)	X																
Urine collection	X																
Pregnancy test (blood)	X																
Pregnancy test (urine)	24 hr before to BCG dose																
General exam and Clinical assessment	X				X*			X*	X*	X*	X*	X*	X*				X
Lymphadenopathy assessment					X*			X*	X*	X*	X*	X*	X*				
BCG injection site evaluation		X	X	X	X	X	X	X	X	X	X	X	X				
Abnormal BCG injection site																	See section 11.3 for procedures
Abnormal BCG injection site clinic visits																	Clinic visits 2x/week from Day 28 ±1 until resolved
Abnormal BCG injection site photos																	Once/week from Days 28 ±1 until resolved
Health status and AE/SAE review		X	X	X	X	X	X	X	X	X	X	X	X	X	X	X	X
Concomitant med review	X					X	X	X	X	X	X	X	X	X	X	X	X
Oral temperature reporting	X																Days 1 - 112 (recorded on Memory Aid eCRF device)
AE/SAE reporting																	Days 1 - 114 (recorded on Memory Aid eCRF device)
Concomitant medication reporting																	Days 1 - 114 (recorded on Memory Aid eCRF device)
ID site pain, tenderness, drainage reporting																	Days 1 - 114 (recorded on Memory Aid eCRF device)
Blood draw	X	X	X	X	X	X			X	X	X	X	X	X		X	X
Skin biopsy					O/S				X/S	O/S		X/S					
Photographs of ID site						X			X	X	X	X	X				X
PPD skin test															X	X	X
Dressing/guaze collection			X	X	X	X			X	X	X	X	X				

* Only if applicable due to medical history and clinical assessment

O = microbiology

X = immunology

S = swab

* Only if applicable due to medical history and clinical assessment

O = microbiology

X = immunology

S = swab

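### No prompted, graded self-report covers the hours between discharge on Day 0, when BCG is injected, and the first diary entry on Day 1

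*Combined protocol and SAP*

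**What the plan says.** Section 11.2 places the BCG injection at clinic visit 2, Day 0. The instructions for the Day 1 to Day 3 visits then give the self-recording window for the survey: "Solicited local and systemic reactions recorded Days 1-114". Unsolicited AEs/SAEs and concomitant medications get the same window. Appendix B repeats it for AE/SAE reporting, medication reporting and injection-site symptoms ("Days 1 - 114 (recorded on Memory Aid eCRF device"). Its oral temperature row runs from Day 1 to Day 112.

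Other parts of the protocol begin on Day 0:

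- Sections 10.4.1 and 11.2, on the Day 0 visit: "Following administration of Tice® BCG, intradermal (ID) site reactions will be assessed for at least 30 minutes".
- Section 11.3: "The BCG injection site evaluations are scheduled from Day 0 to 84±3". Appendix B marks visit 2 for this evaluation and for the health status and AE/SAE review.
- Section 15.3: "Document AEs from Visit 02 (Day 0) through Visit 10".
- Section 15.2.1 counts reactions as AEs: "All AEs, including local and systemic reactions, not meeting the protocol-defined criteria for serious adverse events (SAEs) should be captured on" the data collection form and eCRF.
- Section 15.1 defines solicited events by their following BCG administration, with no Day 1 cut-off.
- Section 10.6.2 has participants record reactions, other events and medications for the whole study.

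Participants are trained on the memory aid before they leave the clinic on Day 0 (section 11.2).

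**The concern.** Safety and tolerability is the first primary objective. Solicited data have value because every participant is asked about the same list of symptoms, each graded on the same scale, on each day of the window. A window that opens the day after the injection leaves the first hours at home outside that process.

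The systemic symptoms are where this matters. Section 5.8.1 says of the flu-like symptoms, including fever and chills, that "generally not feeling well can last 1-2 days". For an episode that short, the remainder of Day 0 can be an appreciable part of the whole. The local lesion evolves over weeks, so a Day 1 start would not hide it.

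Section 18.1 plans descriptive summaries by group, with five participants each and interpretation resting on clinical judgement. Completeness of each participant's record therefore carries the result.

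**Working it through.** The protocol states no figure that this point can reproduce. The check sets each possible source of Day 0 reaction data against the interval from discharge on Day 0 to the first Day 1 entry.

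1. **Clinic observation on Day 0.** It lasts at least 30 minutes and is directed at the injection site. The Day 0 list in section 11.2 contains no systemic assessment after injection. The two Appendix B marks at visit 2 belong to this visit and end with it.

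2. **Participant diary.** As labelled in section 11.2 and Appendix B, it opens on Day 1. Section 10.6.2 implies a wider window but names no start day or Day 0 entry.

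3. **AE documentation from Day 0.** Sections 15.2.1 and 15.3 make an evening reaction on Day 0 reportable once staff learn of it. They do not require anyone to ask about each listed symptom for those hours.

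4. **Day 1 visit.** Staff assess the site and review health status and the events entered on the memory aid. If the diary follows its label, it has no Day 0 entry to review. No symptom-by-symptom question about the previous evening is specified.

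5. **Temperature.** Pulse and blood pressure are marked in Appendix B at screening only. Diary temperature is optional and starts on Day 1. The note to Table 4 in section 15.2.2 takes Day 1 vital signs as baseline, so on a literal reading a fever that began after the injection and persisted into Day 1 would enter the baseline.

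6. **Concomitant medication.** The diary starts on Day 1, and section 11.2 and Appendix B list no staff medication review at visits 2 to 5, although section 10.6.3 asks about medication at every visit. Table 1 uses pain medication to separate Grade 1 from Grade 2 pain, so an analgesic taken on the evening of Day 0 bears on a grade.

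No source provides a prompted, graded record for the interval. Local reactions are partly covered by items 1 and 4; systemic symptoms and fever are covered only if the participant volunteers them.

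For scale only: one reactor recorded as having no reaction changes a group's rate by 1/5 = 20 percentage points, and the pooled rate by 1/10 = 10 points. This is the effect of one such error, not an estimate of how many will occur.

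Direction between groups: section 10.3 starts INH on Day 4 and both groups receive the same BCG injection on Day 0. The gap is the same in both, so it affects the description of BCG tolerability and gives no reason to expect bias in the comparison.

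**The case against.** The strongest reply is that Day 0 is already inside the safety data. Staff look at the site, AE review is marked at visit 2, reactions count as AEs from Day 0, and nothing in section 15.1 or 18.1 excludes them. Participants return the next day, and section 15.2.1 expects events to emerge in visits and interviews. Training before discharge, followed by review of entries on Day 1, suggests that the authors may have meant the diary to begin on Day 0.

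Most of this stands. A reader might infer from the diary label that reactions on the day of injection are left out of the reactogenicity data. The documents do not support that: such reactions are within the AE window and can be recorded. Nor do they say that systemic reactions begin or peak on the evening of Day 0; section 5.8.1 gives a duration only. A one-day reaction starting that evening would often still be present at the Day 1 visit.

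The reply does not supply the prompted record for the interval. If the authors did intend Day 0 use, the labels contradict the intention and should be corrected.

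A further reply is that day numbering may be mixed, given the Table 4 note. The documents do not settle what that note means. Within section 11.2, however, BCG is on Day 0, Day 1 is the next clinic visit, and the diary window appears under that visit, so the label there is hard to read as including the injection day.

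**Conclusion.** The point holds in a limited form. The self-recording window in section 11.2 and Appendix B is narrower than the protocol's own definition of solicited events, its AE start day and its general statement on participant recording. The consequence is a gap in prompted collection from discharge on Day 0 to the first Day 1 entry, chiefly for systemic symptoms and fever. Day 0 events are still reportable.

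The size of any loss cannot be estimated from the documents. A reader might attach a number by supposing, for example, that half of the ten participants react on Day 0 and that 10% to 30% of those reactions are over by the Day 1 entry: 10 × 0.5 × 0.10 = 0.5 to 10 × 0.5 × 0.30 = 1.5 participants. Neither input has a source in the protocol, and the product also assumes that the AE window and the Day 1 visit recover none of them. It should not be used as a finding.

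The conclusion assumes that the labels will be applied as written and that no Day 0 prompt is specified in operational documents outside the protocol. The issue is modest, and correcting it makes the data for the first primary objective more complete.

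**What to change.** In section 11.2, change the three self-recording windows (solicited reactions, unsolicited AEs/SAEs, concomitant medications) from Days 1-114 to Days 0-114. Make the same change in the matching Appendix B rows, and start the oral temperature row, now Days 1-112, on Day 0. State that the first entry is made after discharge on Day 0. State in section 18.1 that reactogenicity is summarised from Day 0. Reconcile the Table 4 note, which takes Day 1 vital signs as baseline, with BCG being given on Day 0.

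The cost is one additional diary entry per participant, ten in all, and a few label edits. Training already takes place before discharge, so no extra visit or instruction is needed.
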